Sponsor/Sponsor- Investigator	[name]. [name]
Study Title	Efficacy and safety of moxidectin and albendazole compared to ivermectin and albendazole co-administration in adolescents infected with Trichuris trichiura : a randomized controlled trial
Short title	Efficacy and safety of MOX/ALB vs. IVM/ALB co-administration
Protocol Number, Date and Version	1, 07.10.2020, v1.1
Trial registration	Will be registered on https://www.clinicaltrials.gov/
Clinical phase	Phase 2 trial
Sample size	540
Indication	Trichuris trichiura infection (eggs in stool)
Investigational Product and Reference Treatment	Moxidectin/ albendazole combination Reference: ivermectin/ albendazole combination
Study Rationale	To provide evidence on the efficacy and safety of co-administered moxidectin and albendazole compared to co-administered ivermectin and albendazole, and to assess the efficacy of the drug combinations compared to monotherapies in adolescents aged 12-19 years against infection with T. trichiura .

Study Objectives	
Our primary objective is to demonstrate non-inferiority of
 
 • Arm A: moxidectin (8 mg) / albendazole (400 mg) combination, compared to • Arm B: ivermectin (200 µg/kg) / albendazole (400 mg) 
in terms of egg reduction rates (ERRs) against T. trichiura infections in adolescents aged 12-19 years assessed at 14-21 days post-treatment by Kato-Katz microscopy.
 
The secondary objectives of the trial are:
 
 a.) to assess superiority in terms of CRs of the drug combinations compared to their corresponding monotherapies: Arm C: Albendazole (400 mg) Arm D: Ivermectin (200 µg/kg) and Arm E: Moxidectin (8 mg) b) to determine the cure rates (CRs) of combination therapies against T. trichiura c) to evaluate the safety and tolerability of the treatment d) to determine the CRs and ERRs of the treatment schemes study participants co-infected with hookworm and A. lumbricoides e) to investigate potential extended effects on follow-up helminth prevalence (5-6 weeks and 3 months post-treatment) of the treatment regimens f) to assess diagnostic performance and compare CRs based on egg counts retrieved from novel diagnostic tools (FECPAK-G2 and/or PCR) compared to standard Kato-Katz microscopy g) to characterize pharmacokinetics (PK) or drug-drug interactions of study drugs following monotherapy or co-administration in T. trichiura infected adolescents. If a dose-response is observed, a Pharmacokinetic/-dynamic (PK/PD) analysis of the study drugs will be performed.
Study design	Randomized controlled trial, open-label with masked outcome assessor
Study product / intervention	Administration of a single oral dose of moxidectin (8mg) / albendazole (400mg)

Comparator(s)	Primary: ivermectin (200 µg/kg) / albendazole (400mg) Secondary: albendazole (400 mg), moxidectin (8 mg) and ivermectin (200 µg/kg) monotherapy
Key inclusion / Exclusion criteria	
Inclusion: Adolescents aged 12-19 years infected with T. trichiura with a minimum count of 48 eggs per gram (EPG) of stool and at least two out of four Kato-Katz slides positive
 
 • having given written informed consent signed by either the participant him/herself (if majority reached; ≥ 18 years) or by caregivers for minors; and written assent by minors (12-17 years) • able and willing to be examined by a study physician before treatment • able and willing to provide two stool samples at baseline and on the three follow-up assessments (14-21 days, 5-6 weeks and 3 months post-treatment), 
Exclusion:
 
 • No written informed consent by individual or caregiver and/or no written assent by minors • Any trial or safety relevant abnormal medical conditions (including severe anemia, body temperature $\geq 38^{\circ}\text{C}$ and or history of acute or severe chronic disease • recent use of anthelminthic drugs (past 4 weeks) • attending other clinical trials during study • known allergy to study medication • pregnancy, lactating or planning to become pregnant within the study period.
Primary Endpoints	ERR against T. trichiura at 14-21 days after treatment derived from EPG assessed by Kato-Katz

Secondary Endpoints	
 • CRs against T. trichiura assessed at 14-21 days post-treatment • CRs and ERRs against A. lumbricoides and hookworm assessed at 14-21 days post-treatment • Adverse events • Infection status and intensity assessed at baseline and 14-21 days post-treatment by novel diagnostic tools (FECPAK-G2 and/or PCR) • Infection status and intensity assessed by Kato-Katz at 5-6 weeks and 3 months after treatment • Characterization of population PK parameters and evaluation of possible drug-drug interactions between moxidectin and albendazole as well as ivermectin and albendazole and possibly PK/PD parameters of all drugs and combinations in T. trichiura infected adolescents
Exploratory Endpoints	None
Interim Analyses	None
Study Duration	6 months total; up to 6 months per participant
Schedule	05/2021 of first-participant in (planned) 11/2021 of last-participant out (planned)
Study centres	Pemba Island (Tanzania)
Measurements & procedures	
Two stool samples will be collected if possible on two consecutive days or otherwise within a maximum of 7 days. The medical history of the participants will be assessed with a standardized questionnaire, in addition to a clinical examination carried out by the study physician before treatment.
 
All participants will be interviewed before treatment and after 3 and 24 hours (active surveillance) and retrospectively again at 14 - 21 days as well as 5-6 weeks and 3 months after treatment about the occurrence of adverse events (AEs). Any potential AEs happening between 24 hours and the respective follow-up time points will be monitored passively and medical intervention as determined suitable by a study physician provided if necessary.

	
The efficacy of the treatment and potential extended effects on follow-up prevalence will be determined around 14 - 21 days, 5-6 weeks and 3 months post-treatment by collecting another two stool samples.
 
All stool samples will be examined with duplicate Kato-Katz thick smears for T. trichiura, A. lumbricoides, and hookworm. From the remaining stool specimen, 3g will be analyzed with the FECPAK-G2 platform and 1.5-2g will be preserved in 70% ethanol and shipped to Swiss TPH, Basel or another reference laboratory for subsequent PCR-analysis.
 
Each participant will be asked to provide a finger-prick blood sample for hemoglobin measurement at baseline. At the same time, anthropometric measurements (i.e. height, and weight) will be taken for all participants. To determine PK/PD parameters of the study drugs, a subsample of 60 willing study participants of all treatment arms will be asked to provide a maximum of 4 micro blood samples using finger pricks at defined time points between day 0 and day 7.

Statistical Analyses	
An available case analysis according to the intention to treat principles will be performed, including all subjects with primary endpoint data. Additionally, a per-protocol analysis will be conducted. Geometric and arithmetic mean egg counts will be calculated for the different treatment arms before and after treatment to assess the corresponding ERRs. Bootstrap resampling method with 5,000 replicates will be used to calculate 95% confidence intervals (CIs) for ERRs and differences between ERRs.
 
CRs will be calculated as the percentage of egg-positive subjects at baseline who become egg-negative after treatment, assessed at 14-21 days with quadruple Kato Katz assays. Differences among CRs (between treatment arms and between diagnostic approaches) will be analyzed by using crude and adjusted logistic regression modelling (adjustment for infection intensity, age, sex and weight). Adverse events will be compiled into frequency tables and compared between treatment groups using descriptive summaries.
 
To determine PK/PD parameters, nonlinear mixed-effects (NLME) modeling will be used. To assess differences in diagnostic performance of the different tools used as compared to the standard Kato-Katz

	microscopy (FECPAK-G2 and/or PCR) a readily available hierarchical Bayesian egg-count model will be applied to the individual level data.
GCP statement	This study will be conducted in compliance with the protocol, the current version of the Declaration of Helsinki, ICH-GCP E6 (R2) as well as all national legal and regulatory requirements.
Key explanation for the inclusion of children	This study will involve adolescents of at least 12 years of age, since an infection with T. trichiura occurs most often in children who are therefore the main target group of deworming campaigns. Younger children will not be included as moxidectin is registered only for children ≥ 12 years.
Recruitment procedure	The trial will be conducted in Pemba (Zanzibar, Tanzania). It will take place in areas with moderate to high T. trichiura endemicity (communities/schools with a prevalence $\geq 25\%$) identified from earlier studies and/or based on experience of the local collaborating team. It will be implemented as a school-based study.
Coverage of damages	Winterthur Police Nr. 4746321, National Insurance Corporation of Tanzania (to be issued)
Storage of data and samples for future research aims	After the study has been completed, all samples will be destroyed. Case report forms and electronic source data will be kept for a minimum of 15 years.
Conflict of interest in relation to the investigated drugs	We declare no conflict of interest in relation to the investigated drugs.

2. Background information

Albendazole and mebendazole are the most widely used drugs for preventive chemotherapy campaigns against soil-transmitted helminth (STH) infections. Albendazole is characterized by high cure rates (CRs) against infections with *Ascaris lumbricoides* (96%) and hookworm infections (80%). Mass drug administration (MDA) with single dose albendazole has already been considered insufficient to achieve World Health Organization (WHO) goals of morbidity reduction, in the case of *Trichuris trichiura* infections due to the low efficacy of this drug (CR 31%) [1, 2].

Therapies combining two or more drugs are widely advocated in different therapeutic areas such as tuberculosis, malaria, HIV/AIDS or cancer. The underlying rationale for multifactorial pharmacological treatment varies with the disease and includes the protection against the selection of drug-resistance, and hence, a prolongation of the life-span of effective and available drugs, and to increase and broaden the efficacy over drugs being administered in monotherapy [3].

To help prioritize candidate STH combinations, the Bill & Melinda Gates Foundation (BMGF) defined different levels of investment risk. In more detail, the prioritization includes four tiers and takes into account (i) the current efficacy and safety data of existing anthelmintic drugs; (ii) the financial and time investment required to generate the necessary evidence to change WHO treatment guidelines; and (iii) the potential for transformational change. The ivermectin/ albendazole combination was identified as a first-tier priority. Moxidectin/ albendazole was classified as second tier priority (since at this stage the drug was not yet approved).

In 2017, ivermectin in combination with albendazole for treatment of STH was added on the Essential Medicines List (EML) paving the way to further evaluate efficacy of this combination among school-aged children and communities in a range of epidemiological settings [4]. While for ivermectin/ albendazole evidence of superiority compared to single standard treatments in different settings and over varying time points is growing [5, 6], we still have very few studies providing similar results for the co-administration of moxidectin and albendazole in STH infections [7].

Moxidectin was recently approved by the Food and Drug Administration (FDA) for the treatment of onchocerciasis at a dose of 8 mg. Our own studies have shown that the combination of moxidectin/ albendazole might reveal high potential in the treatment of STH infections [7, 8]. Moreover, our recent dose-finding study against *T. trichiura* infections revealed that the approved 8 mg dose (regardless whether combined with albendazole or monotherapy) performs as good as higher doses against this STH [9]. However, there is a need to explore whether the longer half-life of moxidectin (compared to ivermectin) could reveal a benefit in the treatment of STH infections [10]. Finally, there is a need to thoroughly evaluate the efficacy of the marketed tablet moxidectin formulation (our previous studies used a different formulation).

In this trial, we test for non-inferiority of both currently approved and available drug combinations (i.e. moxidectin/ albendazole against ivermectin/ albendazole) and for superiority of the combination therapy compared to the respective monotherapies. Furthermore, potential extended effects through a prolonged efficacy assessment scheme in adolescents in Pemba (Tanzania) are examined. Follow-up will be conducted at approx. 14-21 days, 5-6 weeks and 3 months post-treatment to assess co-benefits on worm burden reduction from the relatively long half-life of moxidectin ($T_{1/2}$: 491-832 hours) [11, 12] compared to ivermectin ($T_{1/2}$: 16-32 hours; increasing with age) [13]. Given the comparatively long half-life of moxidectin, the standard follow-up period of 14-21 days recommended by WHO might not be sufficient to reveal the full potential of the drug. Therefore, two more follow-up time points will give the opportunity to investigate potential extended effects on infection status and intensity. Results from this trial will inform decisions on how anthelminthic combination therapy could be introduced into existing MDA programs and, therefore, provide a valuable adjunct tool for interrupting STH transmission.

The pharmacokinetic/-dynamic (PK/PD) characterization of a drug is essential to understand the response of the human body to a drug and vice versa, especially in populations that physiologically differ from healthy adults. Physiological characteristic like mal- or undernutrition or intestinal worms, such as *T. trichiura*, can potentially affect the PK of a drug.[14, 15]. For moxidectin, clinical pharmacokinetics have so far exclusively been assessed in a limited number of healthy adults [16, 17]. A trial currently being conducted by our group will characterize PK and evaluate PK/PD parameters of moxidectin in adults infected with *Strongyloides stercoralis*. Our study will be the first one to provide information on the PK, PK/PD on all three drugs in this population and thus guide optimal drug dosing in *T. trichuris*-infected adolescence in Pemba. Additionally, we aim to provide novel information on the possible interplay of moxidectin and ivermectin with albendazole when co-administered. For this it is necessary to take not only samples in the combination arm but also in the monotherapy arms.

Micro blood sampling by collecting blood from a finger prick has become the preferred method not only for molecular epidemiological studies but also for PK studies due to its minimal invasiveness, and simple and fast handling [18]. Furthermore, the results gained by this method have been repeatedly shown to correlate well with the standard venous blood sampling, which also holds true for ivermectin and albendazole and is currently under investigation for moxidectin by our group [19, 20]. A sparse sampling approach will be used in 60 participants, which allows to use only 4 samples per individual.

3. Trial objective and purpose

We designed a non-inferiority trial to show that co-administered moxidectin and albendazole is non-inferior compared to co-administered ivermectin and albendazole in adolescents aged 12-19 years on Pemba Island (Tanzania). From previous studies conducted by our group, we expect similar efficacies from the combination moxidectin/ albendazole compared to ivermectin/ albendazole [7, 8]. However, moxidectin might be advantageous in terms of the drug's longer half-life and in areas with possible emerging ivermectin resistance [17, 21]. This study will allow comparing the efficacy of the two available co-administrations and will provide further insights on the potential value of moxidectin/ albendazole. Our data will pave the way for possible large scale, multi country follow-up studies. As recommended for new combination therapies, we simultaneously assess superiority of the drug combinations compared to monotherapies.

The **primary objective** is to demonstrate that co-administered moxidectin (8 mg) / albendazole (400 mg) is non-inferior to ivermectin (200 µg/kg) / albendazole (400 mg) in terms of egg reduction rates (ERRs) against *T. trichiura* infections assessed by Kato-Katz at 14-21 days post-treatment in adolescents aged 12-19 years using a non-inferiority margin of 2 percentage-points.

The **secondary objectives** of the trial are:

- a) Efficacy assessments of combination therapies require demonstration of superiority against the respective monotherapies. Therefore, the trial has five different treatment groups: moxidectin (8 mg) / albendazole (400 mg) combination, ivermectin (200 µg/kg) / albendazole (400 mg) combination, albendazole (400 mg) monotherapy, ivermectin (200 µg/kg) monotherapy and moxidectin (8 mg) monotherapy.
- b) to determine the CRs of the drug regimens against *T. trichiura*
- c) to evaluate the safety and tolerability of the treatment
- d) to determine the CRs and ERRs of the treatment schemes in study participants infected with hookworm and *A. lumbricoides*
- e) to investigate potential extended effects on follow-up helminth prevalences (5-6 weeks and 3 months post-treatment) of the treatment regimens
- f) to assess diagnostic performance and compare CRs based on egg counts retrieved from novel diagnostic tools (FECPAK-G2 and/or PCR) compared to standard microscopy
- g) to characterize population PK parameters, as well as drug-drug interactions of active study treatments following single and co-administration in *T. trichiura* infected adolescents. If a dose-response is observed, a PK/PD analysis will further be performed

4. Methodology

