4.3.2 Diagnosis

At baseline, all participants will be asked to provide two stool samples (within a maximum of 7 days). From each stool specimen, duplicate Kato-Katz thick smears (41.7 mg each) [24] will be prepared and read under a microscope for eggs of *T. trichiura*, *A. lumbricoides* and hookworm by experienced technicians. To ensure quality of hookworm diagnosis, 10% of the samples will be divided into two subsamples; one of the containers will keep its original participant ID, whereas the second container will be labeled with a new ID (assigned by the co-PI). Duplicate Kato-Katz will be prepared from both containers and the findings compared. For hookworm, results are considered correct if no difference in presence/absence is found. For quality control of *A. lumbricoides* and *T. trichiura* egg counts, 10% of slides will be re-read by another laboratory technician. Results are considered correct if the following tolerance margin is not exceeded: (i) No difference in presence/absence of *A. lumbricoides* and *T. trichiura* (ii) egg counts are +/-10 eggs for counts \leq 100 eggs or +/-20% for counts $>$ 100 eggs (for each species separately). In case discrepancies above the tolerance margin are noted in one or more slides, the respective slides are re-read by the local technicians. The new results are discussed, so that in case of discordant results, slides can be re-evaluated to reach consensus. The same slides might further be re-read by an automatized reading system (Kato-Katz 2.0) if available at study start.

All microscopically analyzed quadruplicate Kato-Katz thick smears will be destroyed after passing the quality control. Additionally, a portion of 1.5-2 g of stool from each specimen will be preserved in 70% ethanol and shipped to a reference laboratory for polymerase chain reaction (PCR) analysis (to be determined) [25]. The same sampling procedure and diagnostic approach will be applied at days 14-21, 5-6 weeks and 3 months post-treatment. At baseline and 14-21 days post-treatment, 3g of the remaining stool specimen will be used for analysis with a further developed version of the FECPAK-G2 device using a similar laboratory protocol as applied in previous studies [26, 27].

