7.2 Data collection and documentation

Data collected and produced within this trial will fall into one of the following categories:

- a) Egg counts of *T. trichiura*, Hookworm (*Necator americanus* and *Ancylostoma duodenale*, no differentiation between the two species will be made) and *A. lumbricoides* derived from standard Kato-Katz microscopy performed at baseline as well as at 14-21 day, 5-6 weeks and 3 months post-treatment.
- b) Egg counts of *T. trichiura*, Hookworm and *A. lumbricoides* derived from FECPAK-G2 platform analysis at baseline and 14-21 days post-treatment.
- c) Anthropometric and clinical characteristics of the trial participants collected using the study's CRF such as weight, height, blood pressure, temperature, pregnancy status (for female subjects), overall health status and any abnormal medical condition or chronic disease.
- d) PK time recording of each sample per person
- e) Measured concentrations analyzed from micro blood samples and subsequently derived PK/PD parameters
- f) Infection status of *T. trichiura*, Hookworm and *A. lumbricoides* derived by PCR assessment of ethanol-fixated stool sample aliquots

Data of categories c) and d) will be recorded both paper-based and directly into tablets using CommCare (Dimagi, Inc., Cambridge, MA) or a comparable data-entry software, whereas data in categories a), b) and e) will be captured by software only. Data compiled using the software will be directly saved on the personal, password-protected laptop of one of the Co-PIs and uploaded to a server hosted at Swiss TPH, Basel. In paper-based data collection, all missing data must be explained. If an item on the CRF is left blank because the procedure was not done or the question was not asked "N/D" will be entered. If the item is not applicable to the individual case "N/A" will be written. All entries will be printed in black ink. All corrections must be noted with the initials of the respective team member and dated. Data in categories a) and c) will be merged into a masterfile and saved in .xlsx, .mdb and/or .csv. Data in categories b) and d) - f) will be saved as .mdb, .csv, .xlsx, .txt and/or .pdf files. For categories a) – d), paper-based data will serve as physical backup. Hard copies of the data such as parasitological sheets and CRFs will remain at PHL-IdC. Digital copies along with single databases and compiled masterfiles will be transferred to the Swiss TPH, Basel. Data will then be analyzed as described in section 8.

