8.3 Description of statistical methods

In non-inferiority trials, non-inferiority has to be demonstrated in the intention-to-treat and in the per protocol population. The primary analysis will be performed according to the intention-to-treat principles using the available case population which includes all participants with any primary end point data. Subsequently, a per-protocol analysis will be performed. EPG will be assessed by calculating the mean egg count from the quadruplicate Kato-Katz thick smears and multiplying this number by a factor of 24. The ERR will be calculated as:

$$ERR = 1 - \frac{\frac{1}{n} e^{\sum \log(EPG_{follow-up} + 1)} - 1}{\frac{1}{n} e^{\sum \log(EPG_{baseline} + 1)} - 1}$$

Geometric mean egg counts will be calculated for the different treatment arms before and at 14-21 days after treatment to assess the corresponding ERRs. Bootstrap resampling method with 5,000 replicates will be used to calculate 95% confidence intervals (CIs) for ERRs and the difference between the ERRs. CRs will be calculated as the percentage of egg-positive children at baseline who become egg-negative after treatment. Differences among CRs will be assessed by using unadjusted logistic regressions. In a subsequent analysis an adjusted logistic regression (adjustment for baseline infection intensity, age, sex, weight) will be performed.

Questionnaires on physical functioning and treatment satisfaction will be evaluated by creating summary scores by summing up and transforming the single question scores according to the following formula: [(actual raw score-lowest possible raw score)/(possible raw score range)]*100 [40].

Adverse events will be summarized in frequency tables and compared between treatment groups using descriptive statistics.

To assess differences in diagnostic performance of the different tools used as compared to the standard Kato-Katz microscopy (FECPAK-G2 and/or PCR) a readily available hierarchical Bayesian egg-count model will be applied to the individual level data.

A nonlinear mixed-effects (NLME) modelling will be used to determine pharmacokinetic parameters. Concentrations are measured with a validated LC-MS/MS method [20, 31]. Using NLME, the key population PK parameters will be calculated based on which an effect on the drug-drug interaction will be determined:

- C_{\max} maximal plasma concentration
- t_{\max} time to reach C_{\max}
- AUC area under the curve, from 0 to 24h and 0 to inf.
- $t_{1/2}$ elimination half-life

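### Cure-rate differences between diagnostic tools, read on the same participants' stools, are assigned to crude and adjusted logistic regression with no paired or clustered method named; the PCR outcome also needs reconciling

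*Combined protocol and SAP*

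**What the plan says.** **Method.** The synopsis (Statistical Analyses) covers two kinds of comparison in one sentence: "Differences among CRs (between treatment arms and between diagnostic approaches) will be analyzed by using crude and adjusted logistic regression modelling". The adjusted model has "adjustment for infection intensity, age, sex and weight". Section 8.3 says "Differences among CRs will be assessed by using unadjusted logistic regressions", followed by an adjusted version, and does not mention cure-rate comparisons between tools. Both places add that, for diagnostic performance, "a readily available hierarchical Bayesian egg-count model will be applied to the individual level data".

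**Specimens.** The synopsis (Measurements & procedures) says "From the remaining stool specimen, 3g will be analyzed with the FECPAK-G2 platform and 1.5-2g will be preserved in 70% ethanol", after the Kato-Katz smears have been made. Section 4.3.2 agrees: a PCR portion comes from each specimen, and at baseline and 14-21 days "3g of the remaining stool specimen will be used for analysis with a further developed version of the FECPAK-G2 device".

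**Cure rate.** Section 8.3 says "CRs will be calculated as the percentage of egg-positive children at baseline who become egg-negative after treatment" and names no tool. The synopsis gives the same definition but ties it to quadruple Kato-Katz. Under section 5.2 everyone enrolled is Kato-Katz positive for *T. trichiura*.

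**PCR outcome.** Objective f (synopsis and section 3) speaks of egg counts from FECPAK-G2 and/or PCR. The synopsis endpoints and section 4.1 speak of infection status and intensity. Section 7.2(f) lists only "Infection status of *T. trichiura*, Hookworm and *A. lumbricoides* derived by PCR assessment of ethanol-fixated stool sample aliquots", whereas 7.2(b) lists egg counts for FECPAK-G2.

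**The concern.** A comparison between arms has independent groups; a comparison between tools is made within participants. One method is named for both. The listed covariates describe the participant, but they are not a participant term and do not make two readings of one person's stool independent. The synopsis sentence is the only place where a method is assigned to cure-rate differences between tools, so an analyst who follows it literally would stack the readings and discard the pairing.

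Two further gaps affect the same comparison. The plan does not say on which common set of participants two tools' cure rates are compared: all enrolled, or only those also positive at baseline by the second tool. It also describes the PCR result in three ways. Two analysts could therefore report different between-tool results from the same data.

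At stake is the precision and reproducibility of objective f. The primary egg-reduction analysis and the cure-rate comparisons between arms are untouched.

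**Working it through.** The documents give no sample size, expected cure rate by tool or agreement between tools for this comparison, so there is no stated figure to reproduce. The calculation below is an illustration, and every correlation in it is assumed.

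**1. Crude model.** Let n participants each be read by two tools, with equal cure rate p and within-person correlation ρ.

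- Variance of the difference, readings treated as independent: 2p(1−p)/n
- Variance of the difference, pairing respected: 2p(1−p)(1−ρ)/n
- Ratio of SEs: 1/√(1−ρ), whatever p or n
- True two-sided error of the nominal 5% unpaired test: 2·[1−Φ(1.96/√(1−ρ))]

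| Assumed ρ | SE ratio | True type I error |
|---|---|---|
| 0.2 | 1/√0.8 = 1.12 | 2.8% |
| 0.3 | 1/√0.7 = 1.20 | 1.9% |
| 0.5 | 1/√0.5 = 1.41 | 0.6% |
| 0.7 | 1/√0.3 = 1.83 | 0.03% |

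Because the variance ratio is 1−ρ, the unpaired interval at ρ = 0.5 is as wide as a paired interval from half the participants; at ρ = 0.3, from 70% of them. A simulation of the log odds ratio (20,000 replicates, 486 pairs, cure rate 50% by both tools) gave type I errors of 2.1%, 0.6% and 0.03% for the unclustered SE at ρ = 0.3, 0.5 and 0.7. The participant-clustered SE gave 5.3%, 5.1% and 5.2%.

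**2. Adjusted model.** Covariates help only as far as they explain why a participant's two readings agree. A simulation of the stacked, adjusted regression used 486 participants, cure rate 60% by both tools, baseline intensity as the one informative covariate and three with no effect. The ratios of model SE to true SE were:

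| Share of the shared latent variance explained by intensity (assumed) | ρ = 0.2 | 0.3 | 0.5 | 0.7 |
|---|---|---|---|---|
| 30% | 1.09 | 1.14 | 1.31 | 1.65 |
| 60% | 1.04 | 1.09 | 1.19 | 1.45 |

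The excess shrinks but does not disappear. In the same setting, the GEE clustered on participant had a type I error of 5.0-5.3% and McNemar's test 4.9-5.2%.

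**3. PCR outcome.**

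| Place | PCR result described as |
|---|---|
| Synopsis objective f; section 3 objective f | egg counts |
| Synopsis Secondary Endpoints; section 4.1 | infection status and intensity |
| Section 7.2(f) | infection status only |

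These cannot all describe the same variable. Section 7.2 itself separates the tools, with counts for FECPAK-G2 and status for PCR.

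**The case against.** The strongest reply is that this rests on one parenthesis in a synopsis. Section 8.3 does not repeat it, and its only method for comparing tools is the hierarchical model on individual-level data, which could carry the pairing. Logistic regression is also a family: conditional, GEE and mixed versions belong to it, and the text does not state independent errors. Part of this stands. A reader might infer that an unpaired test is definitely planned; the documents show only that no paired or clustered version is named. The reply does not dispose of the point, however. The hierarchical model is assigned to diagnostic performance, its structure is not given, and the synopsis sends cure-rate differences between tools to logistic regression. A crude model, in ordinary use, contains the tool indicator and nothing else.

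Three stronger readings are tempting and are not supported:

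- **False positives.** Under positive correlation the error runs the other way: the test rejects too rarely.
- **A status-only PCR result cannot enter the egg-count model.** This would follow for a pure count likelihood. With the structure unstated, a presence/absence reading could be linked to latent intensity.
- **The comparison must be limited to participants positive by both tools.** All enrolled participants is an equally defensible set. The gap is that no set is stated.

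It is also fair to say that the consequence is modest. One secondary objective is involved, with no stated power, margin or decision rule, and large differences between tools would be detected either way.

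**Conclusion.** The point holds, and the plan should be changed. The only method named for cure-rate differences between tools is the one used between arms. Nothing in the synopsis or section 8.3 accounts for the tools being read on the same stools. If the regression is fitted with independent errors, the SE is too large by a factor of 1.20 at ρ = 0.3 and 1.41 at ρ = 0.5, and by somewhat less after adjustment. These sizes assume positive within-person correlation and, for the formula, equal cure rates; the documents give no value of ρ. The result is a conservative test and intervals that are too wide, confined to objective f.

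The missing common participant set and the conflicting descriptions of the PCR outcome are matters of text and need no statistical assumption. Confidence is high on these and on the absence of a named paired method. It is lower on what the analysts would actually fit.

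**What to change.** 1. Keep logistic regression for cure-rate differences between treatment arms.
2. In both the synopsis and section 8.3, assign cure-rate differences between tools to a paired analysis: McNemar's test with a paired risk-difference confidence interval. Where covariates are wanted or arms are pooled, use a logistic GEE clustered on participant with treatment arm in the model. Say whether the comparison is pooled or by arm.
3. State one common participant set for each tool comparison: either all enrolled, or those positive at baseline by both tools, with the other set as a sensitivity analysis. Say what cure means for each tool, since the synopsis ties it to Kato-Katz.
4. Reconcile the PCR outcome across objective f (synopsis and section 3), the synopsis endpoints, section 4.1 and section 7.2(f). If it is status only, analyse it as a paired binary result and state how, if at all, it enters the egg-count model.

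The cost is wording in the analysis text. Samples, visits and data stay the same, and the primary and between-arm analyses do not change.
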